6.3.4 Questionnaire 3 (28 days after vaccination)

- questions about any events that are open since questionnaires 1 or 2
- questions about any new unsolicited events that have started after completion of questionnaire 2, including any occurrence of fever.
- did your child have changes in medication
- is your child healthy at present
- do you have any other remarks (contact form to be sent to email server; not part of the data collection of the study)
- thank you!

6.4 Reminders

Parents are sent reminders if the filled questionnaire is not received by Lareb.

- after Q1 (day 5), reminder at day 7, valid time of return: day 8
- after Q2 (day 14), reminder at day 16, valid time of return: day 18
- after Q3 (day 28), reminder at day 32, valid time of return: day 36.

Questionnaires received after the valid time of return will not be included in the Per Protocol analysis.

6.5 Measurements

If parents suspect their child to have fever, they are asked to measure body temperature rectally with their own thermometer. It is therefore assumed that all reported temperature values are from rectal measurements. In the current setup of the study there is no possibility to verify if this is actually done. However, we assume that temperature values obtained otherwise, will be similarly distributed over both groups of 'old' and 'new' vaccine recipients.

CHAPTER 7. STUDY PRODUCTS

7.1 Description of study products

All vaccines used in this investigation are regularly licensed products, currently used in the NIP. Their good record of safety and effectiveness is well established. For details of both products, see the SmPC.

NeisVac-C® vaccine is a suspension for injection in a pre-filled syringe of 0,5 ml. It is a conjugated meningococcal group C-polysaccharide vaccine (adsorbed). RVG number 26343. One dose (0,5 ml) contains *Neisseria-meningitidis* polysaccharide (O-deacetylated) of group C (C11-strain) 10 microgram conjugated to tetanus toxoid 10 – 20 microgram, adsorbed to aluminumhydroxide, hydrated 0,5 mg Al₃+. The product further contains sodium chloride and water for injections.

Originally, NeisVac-C® was manufactured in USA. Baxter Ltd has decided to continue production in Austria. The change of production site was approved by EMA, as all in process tests and preclinical tests showed no deviations. License was continued, with the advice that a Post-Authorization Safety Study should be performed, which is the subject of the study described in this protocol.

Baby clinics are randomised and supplied with either product (new vs old production facility, product A vs product B).

Simultaneously, all children are given a MMR (measles-mumps-rubella vaccine, live attenuated).

M-M-R-VAXPRO® powder and solvent for suspension for injection. Measles-Mumps-Rubella vaccine (live). EMA number EU/1/06/337/001.

After reconstitution one dose (0,5 ml) contains:

- Measles virus¹ Enders' Edmonston strain (live, attenuated), no less than 1x10³ CCID50*
- Mumps virus¹ Jeryl Lynn™ [Level B] strain (live, attenuated), no less than 12,5x10³ CCID50*
- Rubellavirus² Wistar RA 27/3 strain (live, attenuated), no less than 1x10³ CCID50*

* 50% cell culture infectious dose.

¹ produced in chicken embryo cells. ² produced in WI-38 human diploid lung fibroblasts.

The vaccine may contain traces of recombinant human albumine (rHA). The vaccine contains traces of neomycine. The vaccine contains 14,5 mg sorbitol, and further sodium phosphate, potassium phosphate, sucrose, hydrolysee gelatin, Medium 199 with Hanks salts, minimum essential medium Eagle (MEM), monosodium L-glutamate, phenol red, sodium bicarbonate, sodium chloride and hydrochloric acid to obtain desired acidity.

At present M-M-R-VaxPro® (Sanofi Pasteur MSD) is used in the NIP. Throughout the present study, it is foreseen that this vaccine is the only brand used. Children may receive any batch of the MMR vaccine, and are not vaccinated with specified batches.

7.2 Description of route of administration and dosage

NeisVac-C® will be injected intramuscularly (one dose is 0,5 ml). MMR will be injected subcutaneously (one dose is 0,5 ml, after reconstitution).

Injection sites are not prescribed in this protocol. The baby clinic personnel is asked to follow their usual practice. Neither the various organisations of child health care, nor the National Immunisation Programme prescribe the injection sites.

After injection, baby clinic staff is asked to write down which vaccine is injected where, and which batch numbers were used. Parents are asked to enter these data into the questionnaires.

7.3 Preparation, packaging, labeling and storage

All study products are packed and labeled according to their license. They are further distinguished by their batch numbers.

Transport and storage are done according to the standards of the NIP.

7.4 Product shipment, accountability

All baby clinics in the study region will receive only one batch of NeisVac-C® during the course of the study (one year). Any next shipment to a baby clinic should ensure that the right batch is delivered. From these shipments, also children who do not participate, will receive their NeisVac-C® vaccinations.

For MMR vaccine, there is no preference for particular batches to be used per clinic.

Throughout the study period, the baby clinics will be (re)supplied regularly (every 2-3 months).

Accountability is not a requirement for this study. However, the number of doses per baby clinic is recorded as part of the usual administration and surveillance of the NIP.

It may occur rarely that vaccines from one baby clinic are transferred to another. Therefore we verify the batch numbers by asking the parents.

CHAPTER 8. STUDY GROUPS, RANDOMISATION AND (UN-) BLINDING

8.1 Study groups

The study comprises of two groups, according to the NeisVac-C® vaccine that has been given. The parents will not be informed which product (old vs new) their child has received.

8.2 Randomization and stratification

Central randomisation: baby clinics are randomly assigned to use either the old or the new NeisVac-C®. Shipments are done according to a distribution list, generated to randomly assign either batch to any participating baby clinic, to ensure that both groups are similar in size, and that local differences in confounding factors (e.g. concurrent infections, habits and attitudes towards vaccinations, ...etc) are balanced out.

RIVM/DVP will generate the distribution list, and will provide the baby clinics accordingly (Appendix 2).

8.3 Study size and recruitment population.

In order to evaluate 1215 children per group according to protocol (see paragraph 9.2) we need to recruit higher numbers of children. The following estimations are done to determine the population size to target for participation. With 1215 per group we need 2430 fully evaluable and complete datasets. We assume that 90% of data from an estimated 2700 respondents that have completed all questionnaires are evaluable. We assume that after starting the questionnaires 75% of responders will also complete the last questionnaire, thus giving an estimation of 3600 responding parents that start and agree to participation. Experience of RIVM indicates that about 40% of parents participate to a similar questionnaire proposal. However, to be sure to include the desired number of respondents we assume a lower percentage: 15-20%. Thus we assume that 18.000 to 24.000 parents need to be addressed for taking part in the investigation. In addition, to compensate for other interferences or loss, we intend to address 25.000 parents.

8.4 (Un) blinding procedure

Not applicable

CHAPTER 9. STATISTICS

9.1 Statistical formulation of the study hypothesis

The primary endpoint in this study is defined as the number of children with fever reactions within 4 days after vaccination with NeisVac-C®. Fever defined as rectally measured 38° Celsius or higher.

Kroesbergen et al found in a study following 863 Dutch children that fever occurred in 46 (5,3%; 95% CI 3,83-8,83) of children at day 0, 1 and/or 2. Fever at days 3 and 4 is not mentioned. A graph shows that the daily prevalence of fever is about max 3,5%. From day 5 the % of children with fever is rising to 19% at day 9 (ascribed to simultaneously given MMR vaccine).

Our primary endpoint is based on pooled daily presence of fever from days 0 to 4 after vaccination. Based on Kroesbergen et al we expect this to occur in about 6% of the children (95% CI 4,44-7,71, when 52/863 cases).

Baby clinics will be randomized to vaccinate with either product

- investigational new product Orth/Donau (Austria) = Active = Group A
- comparator old product Beltsville (US) = Reference = Group B

Randomisation procedure: to be described

9.2 Sample size calculation

For a non-inferiority approach the following assumptions and choices were made:

- null hypothesis: group A receiving the new product, has a higher prevalence of fever than children in group B. The risk ratio between group A and B is 1.5 or more.
- alternative hypothesis (one-sided): the risk ratio between group B and group A is less than 1.5.
- study groups equally sized (approximately)
- type 1 error alpha: rejection null hypothesis when it is actually true, is set at 0,025, one-sided (ICH E9)
- type 2 error beta: rejection null hypothesis, is set at 0,80
- clinically acceptable or meaningful difference between endpoints in group A and group B: risk ratio of 1.5 indicating a higher risk of fever in group A (corresponding with a fever prevalence of 9% in group A).
- sample size is calculated to obtain numbers needed for the Per Protocol Analysis set.

Prior data indicate that the prevalence of fever among the reference group B is about 6%. Sample size was calculated using a web-based sample size calculator Sealed Envelope, based on Blackwelder. We will need to study 1215 children in each group to be able to reject the null hypothesis that the fever rates between in group A are higher than in group B, with probability (power) of at least 0,8. The type I error probability associated with this test of this null hypothesis is 0,05 (two-sided, 0.025% one-sided). If there is truly no difference in fever prevalence between the two groups, then 2430 children are required to be 80% sure that the upper limit of a one-sided 97.5% confidence interval (or equivalently a 95% two-sided confidence interval) of the risk ratio will exclude a difference in favour of the reference group of more than 3%.

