9.6 Statistical methods for data analysis

The primary endpoint of the study, fever cases observed within 4 days after vaccination will be analyzed using logistic regression with vaccination groups ("old" / "new" product) and potential confounders as listed in 5.3 as explanatory factors, applying a log link in order to obtain relative risk estimates at the end. Relative risk and its 95% CI of occurrence of fever cases with the "new" and "old" NeisVac-C® product will be calculated from the regression model assessing a potential increase of fever reactions with the "new" product. If the upper limit of the 95% CI is below 1.5 then the "new" product is considered to be non-inferior to the old one as far as fever reaction is concerned.

The secondary endpoints will be analyzed similarly and descriptive without the non-inferiority considerations.

CHAPTER 10. SAFETY REPORTING

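### Section 9.2 claims at least 80% power from 1215 children per group, but under the risk-ratio rule in 9.6 that number gives about 71%, and 80% needs about 1,500 per group

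*Protocol*

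**What the plan says.** Protocol section 9.2 gives the null hypothesis and the margin as a risk ratio of 1.5, and notes that this corresponds to 9% fever in group A. It sets these planning inputs:

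- Reference rate: "Prior data indicate that the prevalence of fever among the reference group B is about 6"%.
- One-sided alpha of 0.025.
- Power: "with probability (power) of at least 0,8".
- Groups of roughly equal size.
- A web calculator based on Blackwelder.

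The result is "We will need to study 1215 children in each group to be able to reject the null hypothesis". The closing sentence of 9.2 assumes no true difference and says that, with 2430 children, the confidence limit of the risk ratio "will exclude a difference in favour of the reference group of more than 3"%.

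Section 9.6, in agreement with the synopsis, decides on the risk ratio alone: the new product is non-inferior "If the upper limit of the 95% CI is below 1.5".

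Two of the listed design choices in 9.2 are worded wrongly: "alternative hypothesis (one-sided): the risk ratio between group B and group A is less than 1.5", and "type 2 error beta: rejection null hypothesis, is set at 0,80". A later sentence of the same section gives the one-sided error as 0.025% where the list has 0.025.

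**The concern.** A margin of 3 percentage points and a margin of 1.5 on the ratio coincide only if the reference rate is known to be exactly 6%. In the study that rate is estimated. On the ratio scale its error enters multiplied by the margin, so the ratio test needs more children than the difference test. The closing sentence of 9.2 merges the two by speaking of an interval for a risk ratio that excludes a difference. If the size was not worked out for the rule that will be applied, the stated power is not the power of the study.

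The study responds to a regulator's request for active monitoring of the new product against the old one (section 1.1). Too little power raises the chance of an inconclusive answer for two products that are in fact the same. The reversed alternative adds to the confusion: read literally as B over A below 1.5, it does not describe non-inferiority of the new product.

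**Working it through.** **Inputs.** Fever 6% in both groups, no true difference, one-sided alpha 0.025 (z = 1.960), power 0.80 (z = 0.842), equal groups, margin 3 points or ratio 1.5 (all section 9.2). Decision rule from 9.6. Interval for the fever rate, 4.44% to 7.71%, from 9.1. Children are treated as independent throughout. (1.960 + 0.842)² = 7.849; ln 1.5 = 0.4055, squared 0.1644.

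**1. The plan's figure by its named method.** Blackwelder, difference scale:

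n = 7.849 × 2 × 0.06 × 0.94 / 0.03² = 983.7, so 984 per group, not 1215.

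Power of that test at 1215: SE = √(2 × 0.06 × 0.94 / 1215) = 0.00964; 0.03 / 0.00964 − 1.960 = 1.154; power 87.6%.

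**2. Attempts to reach 1215.**

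| Variant | n per group |
|---|---|
| Non-inferiority, 90% power | 1317 |
| Non-inferiority, one-sided 0.05, 80% power | 775 |
| Non-inferiority, one-sided 0.05, 90% power | 1074 |
| Non-inferiority with continuity correction | 1050 |
| Superiority, 6% against 9%, unpooled variance | 1206 |
| Superiority, 6% against 9%, pooled-variance test | 1209 |

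Unpooled superiority: 7.849 × (0.06 × 0.94 + 0.09 × 0.91) / 0.03² = 1206. Only the superiority calculations come within 1% of 1215 (80.2% power at 1215), and they assume a true 3-point difference, whereas 9.2 assumes none. A margin of 2.7 points would also give 1215, but the protocol states no such margin.

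**3. Power of the rule in 9.6.** On the log scale:

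SE(log RR) = √(2 × 0.94 / (0.06 × 1215)) = 0.1606.

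Power = Φ(0.4055 / 0.1606 − 1.960) = Φ(0.565) = 71.4%.

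The Farrington-Manning score formula gives 71.2%, and exact binomial enumeration of the log-ratio interval gives 71.0%.

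**4. Size for 80% under that rule.**

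n = 7.849 × 2 × (0.94 / 0.06) / 0.1644 = 1,496 per group, or about 1,513 by the score formula: about 1,500 per group, 3,000 in total.

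**5. Dependence on the fever rate (ratio rule, 1215 per group).**

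| Common rate | Power |
|---|---|
| 4.44% (lower limit in 9.1) | 58% |
| 6% (planning rate) | 71% |
| 7.5% | 81% |
| 7.71% (upper limit in 9.1) | 82% |

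**6. What recruitment might yield.** Section 8.3: 25,000 parents, 15–20% participation, 75% completion, 90% evaluable.

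25,000 × 0.15 × 0.75 × 0.90 / 2 = 1,266 per group, power 73%.

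25,000 × 0.20 × 0.75 × 0.90 / 2 = 1,688 per group, power 85%.

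**The case against.** The best defence is that 2430 is a minimum. Section 8.3 plans to approach 25,000 parents, and its cautious participation range would give about 73% to 85% power at 6% fever. At the 40% participation that 8.3 reports from experience, the yield is 25,000 × 0.40 × 0.75 × 0.90 / 2 = 3,375 per group and power is about 99%. A reader might infer from the 71% that nearly three in ten such studies of identical products will fail. That holds only if the study ends at the stated minimum. The sizing statement in 9.2 is still wrong, because it ties 80% power to 1215 per group.

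A reader might also infer that 1215 was obtained from a 3-point difference calculation. The text describes it that way, but the named method gives 984 for that margin. The superiority calculation for 6% against 9% is a plausible source; the protocol does not say so, and the origin stays unknown. Were it the source, it would not support the stated power, since it answers a different question.

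The beta of 0.80 and the 0.025% are clerical: the same section gives power of 0.8 and alpha of 0.025 correctly. The null is stated on A to B with the right margin, and 9.6 gives a clear rule. Only the reversed alternative needs correcting for its meaning. Nor does low power raise the chance of wrongly declaring non-inferiority; the rule's margin and confidence level are unaffected.

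**Conclusion.** The point holds for the stated power and size. At 1215 per group and 6% fever in both groups, the rule that decides the study has about 71% power, not at least 80%. It needs about 1,500 per group for 80%, roughly 280 more per group than stated (1,496 − 1,215 = 281). The 3% justification does not yield 1215 either.

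The result rests on the 6% planning rate, no true difference, equal groups, an unadjusted log-ratio interval and independent children. Across the protocol's own interval for the rate, power is 58% to 82%, and it reaches 80% only near 7.5%. Assignment by baby clinic would lower these figures if outcomes within a clinic are positively correlated. The protocol gives no intracluster correlation, so that loss is not quantified here.

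**What to change.** Restate section 9.2 on the scale of the decision rule, for example: *If fever is truly 6% in both groups, 1215 evaluable children per group give about 71% power, before clustering, that the upper 95% limit of RR(A/B) is below 1.5; 80% needs about 1,500 per group.*

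Reword the closing sentence of 9.2 so that it keeps the assumption of no true difference and drops the 3% difference. State the hypotheses as H0: pA/pB ≥ 1.5 against H1: pA/pB < 1.5. As minor edits, give beta as 0.20 and the one-sided alpha as 0.025 (2.5%).

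This costs rewording only, at the price of a less favourable power statement. If the sponsor prefers to keep 80% power, the minimum has to rise from 2430 to about 3,000 evaluable children wherever it appears (synopsis, 4.1, 8.3, 9.2). On the assumptions in 8.3 that means 3,000 / (0.90 × 0.75) = 4,444 starting parents, or 17.8% of 25,000: inside the assumed 15–20%, but not reached at 15%.

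### Section 9.2 claims 80% power for 1215 children per group, but under the protocol's risk-ratio rule the power is about 71%, and 1215 does not follow from the stated inputs

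*Protocol*

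**What the plan says.** Section 9.2 frames the null and alternative hypotheses and the acceptable limit as a risk ratio of 1.5, and notes that this corresponds to 9% fever in group A. The reference rate is given as follows: "Prior data indicate that the prevalence of fever among the reference group B is about 6" per cent. The one-sided type 1 error is 0,025, and the sample size is meant to reject the null hypothesis "with probability (power) of at least 0,8".

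On method, the section says only this: "Sample size was calculated using a web-based sample size calculator Sealed Envelope, based on Blackwelder". It prints no formula. It concludes that 1215 children per group are needed. With no true difference, "2430 children are required to be 80% sure that the upper limit of a one-sided 97.5% confidence interval" of the risk ratio "will exclude a difference in favour of the reference group of more than 3" per cent.

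The decision rule in Section 9.6, repeated in the synopsis, uses the ratio alone: "If the upper limit of the 95% CI is below 1.5 then the" new product is declared non-inferior. Section 8.3 builds the recruitment plan on the same figure: "With 1215 per group we need 2430 fully evaluable and complete datasets".

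**The concern.** A confidence interval for a risk ratio cannot exclude a difference of 3 percentage points. The two limits coincide only if the reference rate is exactly 6%, and even there the two intervals do not give the same power. The 80% claim is attached to the ratio interval, which is the one that decides the study, so it has to hold on that scale.

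If it does not, two identical products have a larger chance of failing the non-inferiority test than the protocol tells its readers. The recruitment steps in Section 8.3 also start from a number that does not deliver the stated power.

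**Working it through.** **Inputs**
- Fever rate p = 0.06 in both groups (Section 9.2; true risk ratio 1).
- One-sided alpha 0.025, z = 1.960 (Section 9.2).
- Power 80%, z = 0.842. The bullet in 9.2 labels 0,80 as the type 2 error, but the paragraph below it calls it power, and I take it as power.
- Equal groups, n = 1215 each (Section 9.2).
- Margins: risk ratio 1.5, ln 1.5 = 0.4055 (Sections 9.2 and 9.6), and 3 percentage points (Section 9.2).
- Range for the rate: 4.44% to 7.71%, the interval for 52/863 in Section 9.1.

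(1.960 + 0.842)² = 7.849.

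**Step 1: can 1215 be reproduced?**
- Difference scale: n = 7.849 × 2p(1−p) / 0.03² = 7.849 × 0.1128 / 0.0009 = 983.7, so 984 per group. Variants with the same inputs also miss 1215: a Farrington-Manning score test gives 1017 and a continuity correction 1050.
- Ratio scale: n = 7.849 × 2(1−p)/p / (ln 1.5)² = 7.849 × 31.33 / 0.1644, about 1496 per group (2992 in total). The Farrington-Manning ratio score method gives about 1513.

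So 1215 falls between the two results and matches neither.

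**Step 2: power of 1215 per group under the Section 9.6 rule**
- SE(log RR) = √(2 × 0.94 / (0.06 × 1215)) = 0.1606.
- Power = Φ(0.4055/0.1606 − 1.960) = 71.4%.
- The Farrington-Manning ratio score method gives 71.2%, and simulation of 500,000 trials gives 71.1%.
- For comparison, a 3-point difference rule at the same n has power Φ(0.03/√(0.1128/1215) − 1.960) = 87.6%.

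**Step 3: dependence on the fever rate (ratio rule, 1215 per group)**

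| Rate in both groups | SE(log RR) | Power |
|---|---|---|
| 4.44% | 0.1882 | 58% |
| 6% | 0.1606 | 71% |
| 7.71% | 0.1404 | 82% |

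Power reaches 80% only at a rate of about 7.3%.

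**Step 4: what the planned recruitment would give**

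Section 8.3 assumes 25.000 letters, 15-20% uptake, 75% completion and 90% evaluable.
- At 15%: 25.000 × 0.15 × 0.75 × 0.90 = 2531 evaluable, about 73% power at 6% fever.
- At 20%: 25.000 × 0.20 × 0.75 × 0.90 = 3375 evaluable, about 85% power.
- Uptake needed for 2992 evaluable: 2992 / (25.000 × 0.75 × 0.90) = 2992/16.875 = 17.7%.

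**The case against.** The best defence is that the study will probably exceed 2430. The synopsis and Section 4.1 call 2430 a minimum, Section 3.3 runs the study for a whole year, and Section 8.3 describes 15-20% uptake as deliberately low against experience of about 40%. At 40%, the same steps give 25.000 × 0.40 × 0.75 × 0.90 = 6750 evaluable children and about 98.8% power. Section 9.3 ties questionnaire deficiencies to the first questionnaire only, so the 75% factor for completing all questionnaires may understate the number evaluable for fever. All of this stands. It means that a reader should not infer that the study as run has a 29% chance of missing the claim; that figure belongs to exactly 2430 evaluable, independent children at 6% fever. It does not rescue the statement in 9.2, which is about 2430. Nor does it cover the plan's own lower bound: at 15% uptake, 2992 evaluable children would need 2992 / (0.15 × 0.75 × 0.90), about 29.551 letters.

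A reader might also infer that a particular difference-scale formula, or an unstated margin of 2.7 points (the value that solves back to 1215), produced the figure. The documents do not show this. An ordinary two-sided comparison of 6% with 9% gives about 1207 to 1209, and other near matches exist.

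Finally, the 3% wording might be read as a second, competing success criterion. It is not one: the hypotheses, the margin bullet, Section 9.6 and the synopsis all use 1.5. The 3% restates 6% against 9%.

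**Conclusion.** Section 9.2 is wrong as written on two counts. The 80% power claimed for 1215 per group is about 71% under the rule that decides the study, and 58% to 82% over the protocol's own range for the fever rate. The figure 1215 follows from the stated inputs on neither scale (984 for a 3-point difference, about 1496 for a risk ratio of 1.5), and its origin is unknown.

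The calculation assumes identical true rates, equal groups, no covariate adjustment and independent children. Clinics are the assigned units (Section 8.2) and the protocol gives no intra-cluster correlation. Any positive value would lower the power, so 71% is an upper figure in that respect and 1496 a lower one. The decision rule itself is not in question.

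**What to change.** In Section 9.2:

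- Replace the derivation with one on the log-risk-ratio scale used in Section 9.6, with its formula and inputs.
- Remove the wording about a 3% difference, so that a risk ratio of 1.5 is the only margin.
- Restate the power at 1215 per group as about 71% at 6% fever, with the range of about 58% to 82% over 4.44% to 7.71%, and note that it assumes independent children.
- Add that the 25.000 letters at 15-20% uptake would yield about 2531 to 3375 evaluable children (about 73% to 85% power at 6%), so 80% is reached only if uptake is about 17.7% or more.

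The change rewrites one paragraph and leaves the decision rule alone. Its cost is a less favourable stated power. At the lower end of assumed uptake, the sponsor must either accept less than 80% or address more parents.
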